3.2 Analysis

Our primary analysis will be an unadjusted generalized linear mixed model that assumes a negative binomial distribution and accounts for groupings of clusters within each hospital. Model terms will include arm (intervention or routine surveillance group), trial period (baseline vs. intervention) and an interaction term between trial period and arm. The assessment of trial success in decreasing the size of clusters will be determined by the significance of the interaction term, which assesses whether the difference in cluster size between the baseline and intervention period differs significantly between the two arms. This model will be used for both the primary and the secondary outcome.

We can write this model symbolically as:

 $\log(y_{ij}) = \beta_0 + \beta_1 Arm_{ij} + \beta_2 Period_{ij} + \beta_3 Arm_{ij} * Period_{ij} + b_{0i} + b_{1i} * Period_i$

where *i* is a hospital, *j* is a signal within the hospital, *Arm* and *Period* are indicator variables and are = 0 for signals in a hospital in the routine surveillance arm or baseline period and 1 if in the intervention arm or period. The b_{0i} and b_{1i} are random effects, and account for the clustering within a given hospital, equivalent to usual length or size of cluster at each hospital. These may differ in the baseline and intervention periods. The ultimate effect of the intervention is assessed through β_3 : as parameterized, if it is negative and has p-value < .05 (or 95% CI excluding 0) then the intervention reduces the size (primary outcome) or duration (secondary outcome) of clusters.

Subsequent analyses will include as-treated and adjusted models. As treated models in this setting correspond to coding hospitals according to whether they actually implemented the WHONET-SaTScan system. All analyses will be performed using current versions of SAS (9.3, as of writing, SAS Institute, Cary NC) and/or R (3.6.1, as of writing).³⁶ These analyses will not be included in formal multiple comparisons adjustment because these are non-independent assessments related to the as-randomized unadjusted analyses. Results will be reported only as estimated effects and confidence limits, in keeping with current recommendations.³⁷ Types of clusters based on pathogen type will be provided as descriptive tables without including statistical analysis.

3.3 Power Assessment

In many settings, an analytic approach to power is possible given that the assumptions of the model (e.g., logistic regression) are met and a relatively simple solution exists. However, generating the expected values to plug in may be difficult. In addition, some settings are complex enough that closed-form solutions may be difficult to generate. Many cluster-randomized designs fall into this class. In cluster-randomized

studies, it is also difficult to obtain reliable estimates of the additional parameters that are required, most notably the between-cluster variance or, equivalently, the intra-class correlation coefficient.

We assessed power using a custom-built simulation/resampling approach. This allowed us to incorporate detailed information from data collected from the hospitals in the study. Briefly, to calculate power by simulation, we 1) generated data under the alternative hypothesis-the data we anticipated seeing; 2) fit the model we planned to fit in the actual study; and 3) recorded whether we rejected the null hypothesis of no detectable effect in the simulated data. We repeated this process many times, and the proportion times we rejected the null hypothesis was used as an estimate of the power under the alternative hypothesis which we used to simulate the data.

Our simulation is based on the actual arm assignments for the trial. For the simulated baseline period in each arm, we use the observed clusters, rather than simulating new clusters; we assume that all clusters are as observed, with a probability of additional cases or days in each arm. In the simulated intervention period, the routine surveillance arm has the observed number of cases from the observed data, while the intervention arm has the effect described below.

We assumed that the intervention would have no effect in 20% of the intervention hospitals. Using the clusters observed in the baseline period within each hospital, we assumed that we prevent 30-50% of the cases after an initial signal during the intervention period in the intervention hospitals, with the actual reduction chosen by a uniform distribution over the described range on a per-outbreak basis. We also assumed that we would shorten the clusters by 50-70% of the observed length after an initial signal in the intervention period in the intervention hospitals. In addition, the extra days and cases added probabilistically to each cluster in the baseline period are not added in the intervention period. Thus, the simulation assumes a secular effect of smaller and shorter clusters.

We then fit the model described above. For our primary analysis, we achieved a power of 100% (95% CI 99.6%,100%) for the main (size) outcome and power of 79% (95% CI 77%, 82%) for the secondary duration outcome. Other assumptions reflected in this estimate include an alpha error level of 0.05.

A Trial of Automated Outbreak Detection to Reduce Hospital Pathogen Spread

NCT#: 04053075

8/15/2019

CLUSTER Project Full Statistical Analysis Plan

[name] August 15, 2019

Background

The CLUSTER (Cluster Linkage Using Statistics to Trigger and Evaluate Response) Trial is a cluster-randomized trial in 82 HCA Healthcare (HCA) affiliated hospitals designed to assess a statistically-based automated method for detecting clusters of hospital acquired infections, compared to routine assessment. The CLUSTER Trial will assess the impact of a space-time statistical software tool, WHONET-SaTScan, on guiding response and containment of hospital-based clusters.

Hospitals have been randomized to:

- **Arm 1**–Routine cluster detection coupled with an evidence-based cluster response protocol
- **Arm 2**–Enhanced cluster detection using an automated cluster detection tool and routine cluster detection, coupled with an evidence-based cluster response protocol

Trial Outcomes

Clusters will be identified based upon WHONET-SaTScan analyses occurring in real time, in both intervention hospitals and in routine surveillance hospitals. The primary outcome is cluster size: the number of cluster cases identified after the initial cluster signal from the WHONET-SaTScan software. The secondary outcome is the cluster duration: the number of days from the initial cluster signal through the last cluster case. WHONET-SaTScan identifies the beginning of a cluster using a p-value threshold, and we define the end of a cluster as the date of the last case meeting the p-value threshold, by the close of the 180 day window, or end of the trial, whichever date is earlier.

Trial outcomes are found in the below table.

Outcome	Metric
Primary Trial Outcome	
Cluster size	Number of cases identified after the initial cluster signal
	through the last cluster case
Secondary Trial Outcome	
Cluster duration	Number of days from the initial cluster signal through
	the last cluster case
Pre-specified secondary exploratory analyses (secondary manuscript)	
Genetic relatedness of clusters	Compare the genetic relatedness of isolates within a
	cluster, defined by the automated cluster detection tool
	or routine cluster detection methods

Analysis

Our primary analysis will be an unadjusted generalized linear mixed model that assumes a negative binomial distribution and accounts for groupings of clusters within each hospital. Model terms will include arm (intervention or routine surveillance group), trial period (baseline vs. intervention) and an interaction term between trial period and arm. The assessment of trial success in decreasing the size of clusters will be determined by the significance of the interaction term, which assesses whether the difference in cluster size between the baseline and intervention period differs significantly between the two arms. This model will be used for both the primary and the secondary outcome.

We can write this model symbolically as:

$$\log(y_{ij}) = \beta_0 + \beta_1 Arm_{ij} + \beta_2 Period_{ij} + \beta_3 Arm_{ij} * Period_{ij} + b_{0i} + b_{1i} * Period_{ij}$$

where *i* is a hospital, *j* is a signal within the hospital, *Arm* and *Period* are indicator variables and are = 0 for signals in a hospital in the routine surveillance arm or baseline period and 1 if in the intervention arm or period. The b_{0i} and b_{1i} are random effects, and account for the clustering within a given hospital, equivalent to usual length or size of cluster at each hospital. These may differ in the baseline and intervention periods. The ultimate effect of the intervention is assessed through β_3 : as parameterized, if it is negative and has p-value < .05 (or 95% CI excluding 0) then the intervention reduces the size (primary outcome) or duration (secondary outcome) of clusters.

Subsequent analyses will include as-treated and adjusted models. As treated models in this setting correspond to coding hospitals according to whether they actually implemented the WHONET-SaTScan system. All analyses will be performed using current versions of SAS (9.3, as of writing, SAS Institute, Cary NC) and/or R (3.6.1, as of writing).¹ These analyses will not be included in formal multiple comparisons adjustment because these are non-independent assessments related to the as-randomized unadjusted analyses. Results will be reported only as estimated effects and confidence limits, in keeping with current recommendations.² Types of clusters based on pathogen type will be provided as descriptive tables without including statistical analysis.

In a secondary paper, we will describe the genetic relatedness among isolates involved in the clusters that are available for whole genome sequencing. Using distance metrics, such as single nucleotide polymorphism-based genetic distance, we will identify those clusters of isolates that are consistent with outbreaks, and compare those clusters identified by WHONET-SaTScan and routine detection methods. Where available, background stains will be used to help define the baseline diversity and to contribute to estimates of the genetic relatedness among isolates involved in clusters.

Power Assessment

In many settings, an analytic approach to power is possible given that the assumptions of the model (e.g., logistic regression) are met and a relatively simple solution exists. However, generating the expected values to plug in may be difficult. In addition, some settings are complex enough that closed-form solutions may be difficult to generate. Many cluster-randomized designs fall into this class. In cluster-randomized studies, it is

also difficult to obtain reliable estimates of the additional parameters that are required, most notably the between-cluster variance or, equivalently, the intra-class correlation coefficient.

We assessed power using a custom-built simulation/resampling approach. This allowed us to incorporate detailed information from data collected from the hospitals in the study. Briefly, to calculate power by simulation, we 1) generated data under the alternative hypothesis-the data we anticipated seeing; 2) fit the model we planned to fit in the actual study; and 3) recorded whether we rejected the null hypothesis of no detectable effect in the simulated data. We repeated this process many times, and the proportion times we rejected the null hypothesis was used as an estimate of the power under the alternative hypothesis which we used to simulate the data.

Our simulation is based on the actual arm assignments for the trial. For the simulated baseline period in each arm, we use the observed clusters, rather than simulating new clusters; we assume that all clusters are as observed, with a probability of additional cases or days in each arm. In the simulated intervention period, the routine surveillance arm has the observed number of cases from the observed data, while the intervention arm has the effect described below.

We assumed that the intervention would have no effect in 20% of the intervention hospitals. Using the clusters observed in the baseline period within each hospital, we assumed that we prevent 30-50% of the cases after an initial signal during the intervention period in the intervention hospitals, with the actual reduction chosen by a uniform distribution over the described range on a per-outbreak basis. We also assumed that we would shorten the clusters by 50-70% of the observed length after an initial signal in the intervention period in the intervention hospitals. In addition, the extra days and cases added probabilistically to each cluster in the baseline period are not added in the intervention period. Thus, the simulation assumes a secular effect of smaller and shorter clusters.

We then fit the model described above. For our primary analysis, we achieved a power of 100% (95% CI 99.6%,100%) for the main (size) outcome and power of 79% (95% CI 77%, 82%) for the secondary duration outcome. Other assumptions reflected in this estimate include an alpha error level of 0.05.

References:

1. R Core Team (2018). R: A language and environment for statistical computing. R Foundation for Statistical Computing, Vienna, Austria. URL http://www.R-project.org/.

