2.3 Study Design and Population

The CLUSTER Trial (Cluster Linkage Using Statistics to Trigger and Evaluate Response) is an 82hospital cluster-randomized trial to evaluate the impact of the WHONET-SaTScan cluster detection system and response protocol on reducing the size and duration of signaled clusters. The study population will include all patients hospitalized at 82 HCA-affiliated hospitals between February 2017 and January 2022 (Table 1).

Table 1. CLOSTER That - Design and Outcomes		
Study Design	Cluster-randomized clinical trial	
Unit of Randomization	Hospitals*	
Study Population	All patients in 82 participating HCA hospitals	
Exclusions	HCA hospitals not in U.S.	
Group Assignments	Routine cluster detection and response protocol for infection prevention programs	
Arm 1 (N=41)	WHONET-SaTScan cluster alerts, routine cluster detection and response protocol for infection	
Arm 2 (N=41)	prevention programs	
Study Period	24-Month Full Baseline Period (Retrospective Data): February 2017 - January 2019 (Note: we will utilize a 24-month lookback period preceding baseline period for the WHONET-SaTScan analysis)	
D : D (
Primary Outcome	Size of cluster (number of cases added to a cluster after the first signal)	
Secondary Outcome	Duration of cluster (number of days from the first signal to the last isolate collection date in a	
	cluster)	
* national layer data will be analyzed by beanited		

Table 1. CLUSTER Trial - Design and Outcomes

* patient-level data will be analyzed by hospital

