2.6 Randomization

Randomization will be performed at the hospital level in order to detect clusters at the hospital and unit levels.⁶³ Randomizing entire hospitals will ensure uniform cluster detection and response practices within each hospital. During randomization, we will evaluate the need to account for hospital case mix using general hospital data (e.g., average daily census, median length of stay, average elixhauser score) and baseline outcome measures (e.g., number of preventable isolates or preventable days), among others, to improve balance across the arms. We will use a novel approach we developed for a prior cluster randomized trial.⁶⁴ In this approach, we will calculate the weighted Mahalanobis distance between pairs of facilities across all key variables for weights representing importance of achieving balance and choose the pairings with the minimum average within-pair distance. We will then assign one member of each pair to each arm.

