2.7 Implementation and Compliance

WHONET-SaTScan will run daily in the intervention arm. Alerts will display in TheraDoc with weekday monitoring by infection preventionists. Alerts will also be accessible to investigators and research coordinators who will follow up with compliance assessments. In the control arm, WHONET-SaTScan will be run daily in the background, on all microbiology and census data in the baseline and intervention period to identify clusters that would have been detected had WHONET-SaTScan been running in real time. The output will be saved to a secure folder to which study staff will have no access. On a monthly basis, a de-identified version of this output will be uploaded to the HCA Research Server for a quality assurance check, to confirm that the program is running appropriately.

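### The as-treated model no longer compares randomised groups and can be biased in either direction; a complier-average estimate that keeps hospitals as randomised should be the main estimate of effect under implementation

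*SAP*

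**What the plan says.** The primary analysis compares hospitals as randomised, through the arm-by-period interaction in a negative binomial mixed model. The SAP (Analysis) and Protocol 3.2 then add: "Subsequent analyses will include as-treated and adjusted models", and explain that "As treated models in this setting correspond to coding hospitals according to whether they actually implemented the WHONET-SaTScan system". These further analyses are left out of multiplicity adjustment because they are "non-independent assessments related to the as-randomized unadjusted analyses", and "Results will be reported only as estimated effects and confidence limits".

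Neither document says what counts as having implemented the system, how a late start or an interruption is coded, or how selection into implementation is handled. No estimate based on assignment is planned for the effect where the tool was used.

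Three design features bear on the point:

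- Hospitals were matched in pairs (Protocol 2.6): "We will then assign one member of each pair to each arm".
- In the control arm the tool runs in the background (Protocol 2.7), and "The output will be saved to a secure folder to which study staff will have no access".
- Both arms use the same response protocol with the same support (Protocol 2.9).

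**The concern.** Implementation is decided after randomisation. Recoding leaves a treated group made up only of hospitals that managed to implement. The control group becomes all of Arm 1, which contains hospitals of both kinds, plus the Arm 2 hospitals that did not implement. Where the Arm 2 member of a matched pair did not implement, both members end up in the same group.

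The model is a difference-in-differences on the log scale, so lasting differences in cluster size between hospitals cancel. Two things do not cancel:

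- **A different trend.** Hospitals that cannot implement may also be on a different course over time, for example because of staffing.
- **Regression to the mean.** If hospitals whose observed baseline clusters happened to be small are less likely to implement, their cluster sizes tend to rise afterwards whatever the tool does.

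This is the only estimate the plan offers of the effect where the tool was in use. It will appear with confidence limits beside the primary result, and readers may take it as the effect of the tool when actually used.

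**Working it through.** **The plan's own figures.** None is given for the as-treated model. The stated power (100% for size, 79% for duration) belongs to the as-randomised model. Its intervals fit about 1,000 simulations: 1000/1000 gives 99.6% to 100%, and 794/1000 gives 76.8% to 81.9%. The power itself cannot be reproduced, because the resampled clusters, the probability of added cases or days, and the variance components are not given.

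**Inputs.** There are 41 hospitals per arm (Protocol Table 1). Let k be the number of non-implementing hospitals in Arm 2, and assume that Arm 1 holds k of the same kind. Let r be the baseline-to-intervention ratio in those hospitals relative to the others. Neither k nor r is in the documents. The range k = 4, 8, 12 is assumed, with k = 8 close to 20% of 41.

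**Formula with no true effect.** The as-treated treated group has 41 − k hospitals, none of the non-implementing kind. The as-treated control group has 41 + k, of which 2k are of that kind. Averaging log changes over hospitals:

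as-treated ratio = exp[−2k·ln(r)/(41 + k)]

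- k = 4, r = 1.25: exp(−(8/45)·0.223) = 0.96
- k = 8, r = 1.25: exp(−(16/49)·0.223) = 0.93
- k = 12, r = 1.25: exp(−(24/53)·0.223) = 0.90

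Other values:

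| k | r = 0.80 | r = 1.10 | r = 1.50 | r = 2.00 |
|---|---|---|---|---|
| 4 | | | 0.93 | 0.88 |
| 8 | 1.08 | 0.97 | 0.88 | 0.80 |
| 12 | | | 0.83 | 0.73 |

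In the as-randomised comparison each arm holds k such hospitals out of 41. Their trend cancels, so both the as-randomised ratio and the complier ratio are 1.00 at every r.

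**Simulation with no true effect.** There were 3,000 runs, with a log-link difference-in-differences and hospital-robust standard errors standing in for the mixed model. Assumed values were a mean of 3 added cases, dispersion 0.8, hospital SDs of 0.4 (level) and 0.2 (period), and 5 and 6 clusters per hospital in the two periods. The percentage is the share of trials whose 95% interval lies wholly below 1 (nominal 2.5%).

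| Who does not implement | As-treated | Complier |
|---|---|---|
| 8 of 41, at random | 0.99 (3.0%) | 0.99 (2.8%) |
| 8 of 41, by stable cluster level | 1.00 (3.2%) | 1.00 (3.2%) |
| 8 of 41, r = 1.5 | 0.86 (13%) | 1.00 (2.6%) |
| 8 of 41, r = 2.0 | 0.76 (29%) | 1.00 (2.2%) |
| 8 of 41, smallest observed baseline clusters | 0.85 (15%) | 1.00 (2.8%) |
| 12 of 41, smallest observed baseline clusters | 0.79 (25%) | 1.00 (2.9%) |
| 8 of 41, r = 0.67 | 1.13 (0.6%) | 1.01 (2.9%) |

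The simulated 0.86 at r = 1.5 is a little below the formula's 0.88 because the model averages means, not logs: 1/[(33 + 16 × 1.5)/49] = 49/57 = 0.86.

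**With a true ratio of 0.60 in implementers and k = 8.** The as-randomised ratio is (33 × 0.60 + 8)/41 = 0.678. The complier estimate is exp[ln(0.678)/(33/41)] = 0.62, so dividing the log ratio is only approximate. Across the simulated scenarios it gave 0.59 to 0.64. The as-treated model gave 0.60 when non-implementation was random and 0.51 when it was selective.

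**Precision.** Under no effect the standard error of the log ratio was about 0.19 as-treated and 0.24 for the complier estimate (0.19 × 41/33 = 0.24). Combined with the bias from the formula, root mean squared error at r = 1.25 is √(0.073² + 0.19²) = 0.20 as-treated against 0.24. At r = 1.5 it is √(0.132² + 0.19²) = 0.23, about equal.

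**The case against.** The strongest reply is that nothing in the trial turns on this model. Success is judged by the as-randomised interaction, the as-treated model is openly described, and leaving the randomised comparison is what the term means. That stands, and it limits the point to a supporting analysis.

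The bias is also conditional. If non-implementation is random or follows only the stable cluster level, the as-treated ratio is about 1.00, and the documents give no evidence of a different trend. Installation runs through a company-wide system (Protocol 2.4), so non-implementers may be few. With k = 1 and r = 1.25 the ratio is exp(−(2/42)·0.223) = 0.99. With none, the two analyses coincide.

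The alternative has weaknesses too. It is less precise, so at a modest trend difference the biased estimate can lie closer to the truth on average. It is approximate when there is a true effect. Replacing yes/no implementation by the share of days on which alerts were live would add the assumption that the log effect is proportional to live time. These points argue against simply swapping one model for the other. They do not argue against adding an estimate that keeps the randomised comparison.

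A reader might also take the power section as giving a non-implementation rate: "We assumed that the intervention would have no effect in 20% of the intervention hospitals". That is a no-effect assumption, and a hospital can implement and see no effect. Likewise, a reader might infer from Protocol 2.7 that Arm 1 hospitals are documented as unable to see the output. The sentence restricts study staff. The design gives Arm 1 no alerts, but that none used the tool is an assumption.

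**Conclusion.** The point holds for the supporting as-treated model only. As planned, the one estimate of effect under implementation is open to confounding by trend and to regression to the mean, in either direction. Under no true effect and r = 1.25 the distortion is 4% to 10% for 4 to 12 non-implementers of 41. It is larger for stronger trends and absent if implementation is unrelated to change or to baseline noise. These sizes rest on assumed values of k and r and on Arm 1 containing the same kinds of hospital, which randomisation supports on average.

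Three stronger readings are not supported:

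- The trial's main conclusion is not at risk, because it rests on the as-randomised interaction.
- The as-treated model need not show a false benefit. It can equally hide a real one.
- The plan does not say that late or interrupted hospitals will be miscoded. It leaves implementation undefined.

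**What to change.** In the SAP (Analysis) and Protocol 3.2:

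1. Define implementation as yes or no per hospital before outcome data are examined, including how late starts and interruptions are coded. Ideally a hospital coded no had no live alerts, because partial exposure among those hospitals would strain the exclusion assumption below.
2. Add a complier-average estimate for size and duration. Keep hospitals as randomised and divide the interaction log ratio by the share of Arm 2 hospitals that implemented. State the assumption that no Arm 1 hospital used the alerts. Take the interval from a bootstrap that resamples matched pairs of hospitals. Name this the main estimate of effect under implementation.
3. Keep the as-treated model, if wanted, labelled as a non-randomised comparison open to confounding.

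The cost is a few lines of text, one further analysis and a record of which hospitals had live alerts, which the documents do not say is kept. Signals are also needed from Arm 2 hospitals that did not implement. Protocol 2.8 calls for signals in both arms, and the primary analysis needs them too.

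The downsides are an interval about 41/33 = 1.24 times as wide as the as-randomised one on the log scale at k = 8, and an estimator that is only approximate. It also assumes that assignment to Arm 2 without implementation does not alter cluster size or duration. The shared response protocol makes that plausible but does not prove it.
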